6.12. Health Outcomes/Quality-of-Life Analyses

Analyses of POEM, DLQI, EQ-5D-5L, PROMIS, and ACQ-5 are described in [Table KGAB.6.11](#) and [Table KGAB.6.12](#).

6.13. Bioanalytical and Pharmacokinetic/Pharmacodynamic Methods

Details of PK/pharmacodynamic (PD) analyses can be found in a separate PK/PD analysis plan.

6.14. Safety Analyses

The planned analyses of safety data will be performed with an intent to maintain consistency with compound level standard safety analyses. These standards are based on internal standards which were informed by Clinical Data Interchange Standards Consortium (CDISC) standards, regulatory guidance (for example, FDA Clinical Review Template), and cross-industry standardization efforts (for example, Pharmaceutical Users Software Exchange [PhUSE] white papers from the Standard Analyses and Code Sharing Working Group provided in the PhUSE Computational Science Deliverables Catalog).

Safety evaluations will be based upon the following safety analysis populations with their associated study periods, unless specified otherwise:

- Safety Population (Induction Period),
- Maintenance Primary Population (Maintenance Blinded Period), and
- All Lebrikizumab Safety Population (Combined Induction and Maintenance Periods, and Combined Induction and Maintenance Periods plus Follow Up Period [selective analysis]).

These analysis populations are fully defined in [Table KGAB.6.1](#) while [Table KGAB.6.2](#) describes the treatment groups, associated study periods, and the comparisons for each analysis population.

For document writing purposes for safety, tests with two-sided p-values less than 0.05 will be referred to as having strong statistical evidence for a treatment difference, unless otherwise noted. However, p-values should not be over-interpreted for these safety analyses. Except for pre-specified hypotheses, they correspond to data-driven hypotheses and hence are only useful as a flagging mechanism.

Not all displays described in this section will necessarily be included in the CSRs. Any display described and not provided in the CSR would be available upon request. Not all displays will necessarily be created as a “static” display. Some may be incorporated into interactive display tools instead of or in addition to a static display. Any display created interactively will be included in the CSR if deemed relevant to the discussion.

6.14.1. Extent of Exposure

Duration of exposure to study treatment will be summarized by treatment group. Drug interruption time period due to the use of systemic rescue therapies will not be removed from study drug exposure calculations as described in compound level safety standards.

The duration of exposure will be calculated as:

$$\begin{aligned} & \textit{Duration of exposure (days)} \\ & = \textit{Date of last visit (scheduled or unscheduled) in the specified Treatment Period} \\ & \quad - \textit{Date of first dose in Treatment Period} + 1 \end{aligned}$$

The number and percentage of patients in each of the following categories will be included in the summaries:

- >0, ≥7, ≥14, ≥30, ≥60, ≥90, ≥112, ≥120 days for Induction Period (for Maintenance Period, use ≥30, ≥60, ≥90, ≥120, ≥150, ≥180, ≥210, ≥240, and ≥252 days). Note that patients may be included in more than 1 category.
- >0 to <7, ≥7 to <14, ≥14 to <30, ≥30 to <60, ≥60 to <90, ≥90 to <120, ≥120 days (for Maintenance Period, use >0 to <30, ≥30 to <60, ≥60 to <90, ≥90 to <120, ≥120 to <150, ≥150 to <180, ≥180 to <210, ≥210 to <240, ≥240 to <252, ≥252).

Additional exposure ranges may be considered if necessary. No p-values will be reported.

The summaries will also include the following information:

- Total exposure in patient years, calculated as:

Total exposure in patient years

$$= \frac{\text{Sum of duration of exposures for all patients in treatment group}}{365.25}$$

- Mean and median total dose. Total dose (in mg) is calculated by the number of active injections taken during the treatment period multiplied by dose. For patients in Safety Population randomized to lebrizumab 250 mg Q2W or patients in Maintenance Primary Population re-randomized to lebrizumab 250 mg Q2W or Q4W, the total dose (in mg) taken during Induction Period or Maintenance Period will be calculated as follows: *Total lebrizumab dose = Total number of active injections (including loading doses, if any) received in Induction Period or Maintenance Period × 250.*
- Total number of injections received will be derived based on the *Study Drug Administration* eCRF page and the response to the question “Did you or a caregiver successfully inject the study drug?” on the Dosing Diary eCRF page.

The exposure for the All Lebrizumab Safety Population during the Combined Induction and Maintenance Periods will be calculated as (Date of last study visit during Treatment Period – Date of first lebrizumab injection + 1 day) calculated for each treatment period where the patient receives lebrizumab and then summed together (this excludes the duration of time that patients are receiving placebo during the Maintenance Period). If a patient was randomized to lebrizumab during Induction Period, then to placebo during Maintenance Period and later on entered escape arm following loss of response (<EASI-50), the patient’s exposure on lebrizumab during Maintenance Period will be calculated (Date of last study visit during Maintenance Period – Date of first injection to resume lebrizumab + 1 day) and will be added to the exposure in the Induction Period.

The exposure for the All Lebrizumab Safety Population during the Combined Induction and Maintenance Periods plus Follow up Period will be calculated as the time between the first dose of LY and the study treatment disposition visit plus any follow-up period.

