### 3. STUDY DESIGN

This is a randomized, double-blind, placebo-controlled, parallel-group study which is 52 weeks in duration. The study is designed to confirm the safety and efficacy of lebrikizumab as monotherapy for moderate-to-severe atopic dermatitis utilizing a 16-week induction treatment period and a 36-week maintenance treatment period (Figure 1).

Eligible adult and adolescent ( $\geq 12$  to  $< 18$  years weighing  $\geq 40$  kg) patients with moderate-to-severe AD for at least one year, defined according to the American Academy of Dermatology Consensus Criteria, an EASI Score of  $\geq 16$ , an IGA score of  $\geq 3$  and a BSA of  $\geq 10\%$  will be enrolled.

During the 16-week Induction Period, approximately 400 patients will be stratified and randomized 2:1 to either 250 mg lebrikizumab (loading dose of 500 mg given at Baseline and Week 2) or placebo by SC injection Q2W. All study drug injections will be administered in the clinic.

After completion of the Week 16 visit, patients who have responded to treatment [defined as having an IGA of 0 or 1 or a 75% reduction in EASI from Baseline to Week 16 (EASI-75)] will enter the Maintenance Period and will be re-randomized 2:2:1 to one of the following treatment groups: lebrikizumab 250 mg Q2W, lebrikizumab 250 mg Q4W, or placebo Q2W. Patients will be instructed to self-administer study drug at home.

Patients who do not achieve an IGA of 0 or 1 or an EASI-75 at Week 16 and those patients not maintaining an EASI-50 response following re-randomization at Week 24, 32, 40 or 48 will be assigned to an Escape Arm and receive lebrikizumab 250 mg as open-label treatment Q2W through Week 52. Patients not achieving an EASI-50 response after 8 weeks of treatment in the Escape Arm will be terminated from the study.

Efficacy will be measured through the IGA, EASI, BSA, SCORAD, Pruritus and Sleep-loss scores.

Safety will be assessed by monitoring adverse events, serum chemistry, hematology and urinalysis laboratory testing, physical examination, pulse and blood pressure. An independent Data Safety Monitoring Board will monitor patient safety by conducting formal reviews of accumulated safety data periodically throughout the trial. Additionally, adolescents will be monitored for hormones.

Quality of life and impact of disease will be assessed using the POEM, DLQI/CDLQI, EQ-5D and PROMIS Anxiety and Depression measures. Patients reporting comorbid asthma at study entry will complete the ACQ-5.

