### 3.1. Duration of the Study

The total duration of a patient's participation in this study will be approximately 66 weeks (Screening: maximum duration of 30 days; Induction Period: 16 weeks; Maintenance Period: 36 weeks; Follow Up: 12 weeks from last dose at Week 50).

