### **9.13. Sample-Size Determination**

For FDA:

In the DRM06-AD01 Phase 2b study, the proportion of patients who achieved an IGA score of 0 or 1 at Week 16 using the rescue medication non-response sensitivity analysis was approximately 34.7% for lebrikizumab 250 mg Q2W versus 7.7% for placebo. A sample size of 96 for lebrikizumab 250 mg Q2W versus 48 for placebo will have more than 95% power to detect a statistically significant difference with a significance level of .05. However, to ensure sufficient safety information is collected and to ensure sufficient responders for the Maintenance

Period, the sample size will be increased to approximately 400 in total with a randomization ratio of 2:1 lebrikizumab:placebo.

For EMA:

In the DRM06-AD01 Phase 2b study, the proportion of patients who achieved an IGA score of 0 or 1 at Week 16 using the rescue medication non-response sensitivity analysis was approximately 34.7% for lebrikizumab 250 mg Q2W versus 7.7% for placebo, and the proportion of patients who achieved an EASI75 at Week 16 using the rescue medication non-response sensitivity analysis was approximately 48.0% for lebrikizumab 250 mg Q2W versus 11.5% for placebo.

A sample size of 96 for lebrikizumab 250 mg Q2W versus 48 for placebo will have more than 95% power to detect a statistically significant difference with a significance level of .05 for each of the co-primary endpoints, which imply and overall power of at least 90%.

However, to ensure sufficient safety information is collected and to ensure sufficient responders for the Maintenance Period, the sample size will be increased to approximately 400 in total with a randomization ratio of 2:1 lebrikizumab:placebo.

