5.1.3. Maintenance Period (Week 16 to Week 52 [36 Weeks])

5.1.3.1. Maintenance Blinded Period

After completion of the Week 16 visit, patients who have responded to treatment (defined as having an IGA of 0 or 1 or a 75% reduction in EASI from Baseline to Week 16 [EASI-75] according to IWRS system) will enter the Maintenance Period and will be re-randomized 2:2:1 to one of the following treatment groups: lebrikizumab 250 mg Q2W, lebrikizumab 250 mg Q4W, or placebo Q2W. Throughout the maintenance blinded period, patients will receive placebo, as appropriate, to maintain the study blind across treatment groups.

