Maintenance W16 Escape Population	Including patients who were NOT re-randomized to Lebrikizumab 250 mg Q2W, Lebrikizumab 250 mg Q4W or placebo but assigned to escape arm at Week 16, and received at least one dose of study treatment during the maintenance period. Selective efficacy analyses for the maintenance period will be conducted on the Maintenance W16 Escape Population.
Maintenance W24-48 Escape Population	Including patients from Maintenance Primary and Secondary Population who escaped to Lebrikizumab 250 mg Q2W due to EASI-50 non-response at Week 24, 32, 40 or 48. Selective efficacy analyses for the maintenance period will be conducted on the Maintenance W24-48 Escape Population
All Lebrikizumab Safety Population	All randomized patients who received at least 1 dose of lebrikizumab treatment during Combined Induction and Maintenance Periods. Safety analyses for the Combined Induction and Maintenance Periods will be conducted on All Lebrikizumab Safety Population. Selective safety analyses for the Combined Induction and Maintenance Periods plus the follow-up Period will be conducted on All Lebrikizumab Safety Population.

Abbreviations: EASI = Eczema Area and Severity Index; IGA = Investigator Global Assessment;

Table KGAB.6.2. Treatment Groups and Comparisons for Each Study Period and Analysis Population

Study Period	Analysis Population	Treatment Groups	Abbreviation	Inferential Comparisons When Applicable
Induction Period	ITT; Safety	Placebo; Lebrikizumab 250 mg Q2W	PBO; LEB250Q2W	LEB250Q2W vs PBO
Maintenance Blinded Period	Maintenance Primary Population	Lebrikizumab_Res/Placebo; Lebrikizumab_Res/Lebrikizumab 250 mg Q4W; Lebrikizumab_Res/Lebrikizumab 250 mg Q2W; Total Lebrikizumab_Res/ Lebrikizumab (Safety analysis only)	LEB_Res/PBO; LEB_Res/LEB250Q4W; LEB_Res/LEB250Q2W; Total LEB_Res/LEB (Safety analysis only)	LEB_Res/LEB250Q4W vs LEB_Res/PBO; LEB_Res/LEB250Q2W vs LEB_Res/PBO
Maintenance Blinded Period	Maintenance Secondary Population	Placebo_Res/Placebo; Placebo_Res/Lebrikizumab 250 mg Q4W; Placebo_Res/Lebrikizumab 250 mg Q2W	PBO_Res/PBO; PBO_Res/LEB250Q4W; PBO_Res/LEB250Q2W	No Between-Group or Overall Comparisons
Maintenance Escape Period	Maintenance W16 Escape Population	Lebrikizumab_NonResp/ Lebrikizumab 250 mg Q2W; Placebo_NonResp/Lebrikizumab 250 Q2W	LEB_NonResp/ LEB250Q2W; PBO_NonResp/ LEB250Q2W	No Between-Group or Overall Comparisons

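### The plus-follow-up exposure rule in SAP 6.14.1 counts maintenance placebo time as lebrikizumab exposure, which the rule just before it excludes

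*SAP*

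**What the plan says.** SAP Table KGAB.6.1 defines the All Lebrikizumab Safety Population as "All randomized patients who received at least 1 dose of lebrikizumab treatment during Combined Induction and Maintenance Periods". SAP Table KGAB.6.2 lists it for two windows, the combined periods and the combined periods plus follow-up, each with the single group Any Lebrikizumab.

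SAP 6.14.1 then gives each window its own exposure rule:

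- **Combined periods.** Duration is computed for each period in which the patient receives lebrikizumab and then summed; "this excludes the duration of time that patients are receiving placebo during the Maintenance Period". A patient who goes from lebrikizumab to placebo and then escapes has the clock restarted at the injection that resumes lebrikizumab.
- **Combined periods plus follow-up.** Exposure is "the time between the first dose of LY and the study treatment disposition visit plus any follow-up period". Placebo is not mentioned.

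Protocol Table 2 shows that lebrikizumab responders re-randomized to placebo receive only placebo injections from Week 16 to Week 50.

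**The concern.** The population and treatment group are the same in both windows, and SAP 6.1.5 carries over the baseline definition of 6.1.4. A reader would therefore expect the second total to exceed the first by follow-up time only. As written, it also picks up the placebo interval that the first rule removes. Under the same section's patient-years formula, that interval would be reported as lebrikizumab patient-years. Two totals for one population would then differ for a reason the SAP never states, and the larger would overstate time on drug.

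**Working it through.** The documents state no exposure total and no expected escape, termination, dropout or rollover rates. There is no figure to reproduce, and the size has to be built from planning inputs plus stated assumptions.

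**Inputs**
- Protocol 3: "approximately 400 patients will be stratified and randomized 2:1", so about 266.7 patients start on lebrikizumab and 133.3 on placebo.
- Protocol 3.1: "Induction Period: 16 weeks; Maintenance Period: 36 weeks" and "Follow Up: 12 weeks from last dose at Week 50".
- SAP 5.1.3.1: responders "will be re-randomized 2:2:1 to one of the following treatment groups", so one fifth go to placebo.
- Protocol 9.13, Phase 2b EASI-75: "approximately 48.0% for lebrikizumab 250 mg Q2W versus 11.5% for placebo". This is used as the responder rate (assumption). The plan's responder definition is IGA 0/1 or EASI-75, so the EASI-75 rate alone is a lower bound for it.

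**Placebo time wrongly counted** (nobody escapes, nobody drops out)
- Patients: 266.7 × 0.48 × 1/5 = 25.6
- Time: 25.6 × 36 = 921.6 person-weeks; × 7/365.25 = 17.7 patient-years

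Placebo-induction responders re-randomized to placebo add nothing, because their clock starts only at a first lebrikizumab dose.

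**True lebrikizumab time, same case (person-weeks)**
- Induction: 266.7 × 16 = 4,266.7
- Lebrikizumab responders kept on drug: 128 × 0.8 × 36 = 3,686.4
- Lebrikizumab non-responders in escape: 138.7 × 36 = 4,992
- Placebo non-responders in escape: 118 × 36 = 4,248
- Placebo responders re-randomized to lebrikizumab: 15.33 × 0.8 × 36 = 441.6
- Total: 17,634.7 person-weeks = 338.0 patient-years

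Excess: 921.6 / 17,634.7 = **5.2%**.

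**With follow-up for everyone.** The population is 400 − 15.33/5 = 396.9. Adding 12 weeks each gives 4,763 person-weeks, and 921.6 / 22,397.9 = 4.1%. Adding only the 10 weeks beyond Week 52 gives 4.3%.

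**Other assumptions.** If the mean placebo time is *w* weeks and the rest of maintenance is spent on lebrikizumab in escape, the excess is 25.6*w* / [17,634.7 + 25.6(36 − *w*)]. If a share *t* of the 256.7 Week 16 escape patients is terminated at 8 weeks, the denominator falls by 256.7 × 28 × *t*.

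| Assumption | Excess |
|---|---|
| *w* = 8 (all escape at Week 24) | 1.1% |
| *w* = 16 | 2.3% |
| *w* = 24 | 3.4% |
| *w* = 30 | 4.3% |
| *w* = 36, *t* = 30% / 50% | 6.0% / 6.6% |
| *w* = 24, *t* = 30% / 50% | 3.9% / 4.3% |
| 10% dropout in each period | 5.1% |
| Responder rates 34.7% / 7.7% (IGA only) | 3.7% |
| Responder rates 55% / 15% (assumed) | 6.0% |

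The arithmetic ceiling is 9.4%. It treats IGA and EASI-75 responders as separate people (34.7 + 48.0 = 82.7% and 7.7 + 11.5 = 19.2%).

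**The case against.** The strongest reply is that the second rule defines a different quantity. The placebo exclusion is written for the combined periods only. Follow-up is off drug for everyone, so a figure that includes it cannot be pure time on drug, and it can be read as observation time since first dose. That clock may even fit the events better: nothing in SAP 6.1.1, 6.1.4, 6.1.5 or 6.14.2 removes events arising on maintenance placebo from the All Lebrikizumab tables, so trimming placebo time from person-time alone would put the two on different bases.

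Part of this stands. The two rules cover different windows, so they are not two values of one quantity, and any fix must keep events and person-time together. The reply does not rescue the text, because the SAP calls the quantity exposure, in the Extent of Exposure section, and gives no reason for the change. The compound level safety standards might explain the intent, but they are not available here and no SAP text resolves the point.

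A reader might also infer that adverse event rates will be diluted. The documents do not support that. SAP 6.14.2 plans numbers and percentages of patients, Protocol 9.11 uses patient counts as the denominator, and SAP 6.19 reports patients at risk, patients affected and event counts. Patient-years appear only as a descriptive total.

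**Conclusion.** The point holds as a minor inconsistency with a cheap correction. Followed literally, the plus-follow-up rule reports up to 36 weeks of placebo per affected patient as lebrikizumab exposure.

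On the Phase 2b EASI-75 rates the amount is at most about 17.7 patient-years. The 5% figure needs every placebo patient to stay on placebo to Week 52 and nobody to drop out; escape at Week 24 brings it to about 1%, and early termination in the escape arm takes it to 6.6%. With follow-up for all it is about 4%. None of these percentages is a figure from the documents.

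It would be wrong to conclude that the trial's main lebrikizumab exposure is overstated. The combined-period total already excludes placebo time. SAP 6.1.4 lists an exposure summary for that window, whereas 6.1.5 plans only selective adverse event summaries once follow-up is added.

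**What to change.** In SAP 6.14.1, define plus-follow-up exposure as the combined-period exposure, with maintenance placebo time excluded, plus follow-up time after the last lebrikizumab interval. Follow-up that comes only after maintenance placebo should not be added: it lies further from active drug than the placebo weeks being removed.

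In the All Lebrikizumab adverse event tables, flag or separate events that start during maintenance placebo, so that events and person-time are on one basis. If a continuous clock is also wanted, report it as observation time since first dose and do not call it exposure.

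The cost is one or two SAP sentences, a small programming change and a slightly smaller exposure total. Study conduct and the efficacy analyses are untouched.

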6.14.2. Adverse Events

A TEAE is defined as an event that first occurred or worsened in severity after baseline. The MedDRA Lowest Level Term (LLT) will be used in the treatment-emergent computation. The maximum severity for each LLT during the baseline period will be used as baseline. The treatment period will be included as postbaseline for the analysis. For events with a missing severity during the baseline period, it will be treated as ‘mild’ in severity for determining treatment-emergence. Events with a missing severity during the postbaseline period will be treated as ‘severe’ and treatment-emergence will be determined by comparing to baseline severity. For events occurring on the day of first taking study medication, it will be assumed to be posttreatment.

The planned summaries for adverse events are provided in [Table KGAB.6.13](#), and are described more fully in compound level safety standards and in the adverse event-related PhUSE white paper [Analysis and Displays Associated with Adverse Events: Focus on Adverse Events in Phase 2-4 Clinical Trials and Integrated Summary Document (PhUSE 2017)].

Summary tables as described in [Table KGAB.6.13](#) will be presented for the following periods/analysis populations as indicated. Summary tables will include the number and percentage of patients reporting an event. For events that are gender-specific (as defined by MedDRA), the number of participants at risk will include only patients from the given gender.

- Induction Period (Safety Population, S)
- Maintenance Blinded Period (Maintenance Primary Population, M)
- Combined Induction Period and Maintenance Period, Combined Induction and Maintenance Periods Plus Follow-Up Period [selective analysis] (All Lebrizumab Safety Population, A)

Table KGAB.6.13. Summary Tables/Listing Related to Adverse Events

Analysis	Population (Section 6.1.1)
Overview of AEs	S, M, A
Summary of TEAE by PTs	S, M
Summary of TEAE by PTs occurring in $\geq 1\%$ of patients	S, M
Summary of TEAE by PTs within SOC	S, M, A
Summary of TEAE PTs by maximum severity	S, M
Summary of SAE by PT within SOC	S, M, A
Summary of AEs leading to treatment discontinuation by PT with SOC	S, M, A
Summary of TEAE possibly related to study drug by PTs within SOC	S, M
Listing of SAEs (including Death)	ITT
Listing of primary AEs leading to study treatment discontinuation	ITT
Listing of TEAE (for Japan submission only)	S

Abbreviations: A = All Lebrizumab Safety Population; AE = adverse event; ITT = Intent-to-Treat; M = Maintenance Primary Population; PT = Preferred Term; SAE = serious adverse event; S = Safety Population; SOC = System Organ Class; TEAE = treatment-emergent adverse event.

Statistical comparisons will be performed for Safety Population and Maintenance Primary Population using Fisher's exact test. Odds ratio will be provided.

6.14.2.1. Common Adverse Events

The number and percentages of patients with TEAEs will be summarized by treatment using MedDRA PT for the common TEAEs (occurred in $\geq 1\%$ before rounding in total LY column in the table).

